SAINT LUKE'S HOSPITAL
RESEARCH PROTOCOL INVOLVING HUMAN SUBJECTS

Version date: 03/07/2018

Principal Investigator: [name]

Study Title: Vascular Closure for Cardiac Ablation Registry (VACCAR)

Co- Investigator(s): [name]

I. Purpose, Background and Rationale

A. Aim and Hypotheses

Vascular Closure Devices (VCD) have been used to achieve hemostasis of arterial access sites following cardiac catheterization procedures. There is extensive literature available supporting the use of these devices for arterial access site closure, showing reduced time to hemostasis, earlier ambulation and reduced length of hospital stay in comparison to manual compression which is the traditional approach to achieve access site hemostasis. In contrast, there is not significant evidence supporting the use of these devices for closure of femoral venous access site, partly due to limited use of VCD in cardiac electrophysiology procedures, such as catheter ablation for atrial fibrillation and atrial flutter. Another alternative to manual compression, the Figure of 8 stitch has also been used to achieve vascular closure follow catheter ablation of atrial fibrillation and atrial flutter, however it has not been studied formally.

The aim of this registry is to better understand the 'real-world' utilization of VCD or Figure of 8 stitch(F08S) in cardiac ablation procedures and to understand any potential difference between VCD or F08S and manual compression. The outcomes of interest are vascular access site complication rate, time to ambulation and patient perception of pain and overall satisfaction, which is assessed via a survey. The hypothesis of this registry is that there will be an increased patient satisfaction and decreased rate of vascular and bleeding complications with use of either Perclose Proglide system or Figure of 8 stitch for venous closure post atrial fibrillation ablation and atrial flutter ablation procedures in comparison to standard manual compression.

B. Background and Significance

Vascular access site complications are an important cause of morbidity following cardiac catheterization procedures. These include recurrent access site bleeding, hematoma

formation, pseudoaneurysm, arterio-venous fistula, acute vascular thrombosis and distal embolization. Manual compression (MC) for 15- 30 minutes has been the 'gold standard' in achieving hemostasis of the access site after these procedures. However, this approach is limited by the need for transient interruption of heparin anticoagulation to perform sheath removal, prolonged bed rest of several hours post sheath removal, patient discomfort, and increased time demand for health care providers to perform manual closure. Vascular Closure Devices (VCD) were introduced into clinical practice in the mid-1990s with the aim of reducing access site bleeding associated with percutaneous coronary intervention procedures. [1]

Several trials, involving patients who had arterial access, have demonstrated increased efficacy of VCD in comparison to MC as evidenced by a reduced time to hemostasis, earlier ambulation and reduced length of hospital stay. However, there are two studies that demonstrated an increased risk of vascular complications associated with use of these vascular closure devices, in particular groin hematoma and arterial pseudoaneurysm.[2,3] A larger meta-analysis that included 30 studies involving 37,066 patients concluded that the risk of complications was dependent upon the specific vascular closure device used and whether the procedure was a diagnostic catheterization or a percutaneous coronary intervention. In the overall analysis, these studies demonstrate a 2.25 fold increase in risk of complications with a VCD.[4]

Despite this finding, the size of each of these individual trials included in the meta-analysis was modest (100-500 patients) and these studies were not powered for safety end points such as access site bleeding and pseudoaneurysm. Hence, it is difficult to draw conclusions about safety end points from this meta-analysis. To address this issue, recently, a large multicenter randomized controlled trial (RCT) compared VCD to MC and concluded that VCD was non-inferior in terms of vascular access site complications and was associated with reduced time to hemostasis.[5,6]

There have been only a few studies assessing patient comfort and satisfaction with VCD. A RCT showed VCD to be associated with greater patient satisfaction compared to compression. It also allowed for earlier hemostasis and ambulation compared with both compression and VCD. [9] A study comparing one brand of VCD with compression showed significantly increased patient comfort, assessed by visual analogue scales, with VCD use. [10] A prospective study involving 1500 patients undergoing PCI procedures, followed by access site closure with MC, or two brands of VCD showed that patients treated with 1 brand (Angio- Seal) reported greater overall satisfaction, better wound healing and lower discomfort in comparison to the other brand of VCD (Perclose Proglide) and MC.[11] Overall, the increase in patient satisfaction and decreased time to hemostasis with VCD use,

with no significant increase in complications provided a sound rationale for use of VCD over MC in daily clinical practice for arterial closure.

In contrast to the arterial access studies summarized above, only a few small scale studies assessing the use of VCD for femoral venous access closure site have been published. A retrospective analysis of 26 patients undergoing deployment of VCD following cardiac electrophysiology procedures, published in 2015, showed successful deployment of 75 out of 76 vascular closure devices and they were no complications reported. [7] Another study involving 761 VCD deployments in the femoral vein following catheter ablation for atrial fibrillation procedure showed no significant reduction in vascular or non-vascular bleeding rate in comparison to MC. [8]

Catheter ablation for treatment of atrial fibrillation/atrial flutter is a commonly performed procedure involving placement of 3 or 4 large (8-14 French) sheaths in the femoral vein. The procedure is performed on uninterrupted anticoagulation, which indicates that for warfarin and rivaroxaban the procedure is performed without holding any doses of anticoagulant medication. For apixaban, dabigatran and edoxaban, the procedure is performed with holding the dose of anticoagulant the night before the procedure and the morning of the procedure. The current standard of care is that at the conclusion of atrial fibrillation or atrial flutter ablation procedure, all venous sheaths are kept in place and the patient is transported to a recovery unit. Upon arrival in the recovery unit, the nursing staff will assess the ACT. Sheaths are not removed via manual compression until the ACT is < 165 seconds. During this time period, which may take several hours, the patients are lying flat on their back with their legs straight. Once the ACT is <165 seconds, the nurses will apply manual compression for 15 to 20 minutes. Following hemostasis, the patients lie flat with their legs straight for 3-4 hours. At that point, the access sites are rechecked to ensure hemostasis, and then the patient is allowed to ambulate.

In contrast, the patient receiving a vascular closure device (VCD) undergoes sheath removal at the conclusion of the procedure and hemostasis is achieved before the patient is removed from the table. When the patient is transported to recovery, they must lie flat on their back for 1 hour and then they are permitted to ambulate, irrespective of their ACT. Both patients receiving MC and VCD are monitored overnight for any post op complications such as recurrent bleeding, hematoma, pain or swelling from vascular access site.

Similarly, the Figure of 8 stitch has been used to achieve vascular closure following procedures involved access to the femoral vein, including leadless pacemaker implantation as well as catheter ablation of atrial fibrillation and atrial flutter. The process involves placing 0 silk suture through the skin and subcutaneous tissue below the lowest venous

access site and then through the skin and subcutaneous tissue above the highest venous access site in a Figure of 8 pattern. The Figure of 8 stitch requires administration of protamine a few minutes prior to sheath removal, removing the sheaths and the tying the 0 silk suture which pulls together the skin and tissue above and below the access site and then holding pressure at the groin for 5 minutes after application of the F08S. The following day, the F08S has to be cut prior to discharge. In a study of 200 patients undergoing cryoablation, patients were allocated to receive manual compression or F08S. There was no significant difference in incidence of hematoma or re-bleeding at the access site between the two groups [12].

It is not known if routine use of VCD or F08S would lead to increased patient satisfaction, earlier ambulation, earlier discharge and decreased rate of complications.

This registry is Investigator initiated.

C. Rationale

The rationale of this registry is to better understand the 'real-world' utilization of VCD and F08S in cardiac ablation procedures and to understand any potential difference between VCD/ F08S and manual compression. The outcomes of interest are vascular access site complication rate, time to ambulation and patient perception of pain and overall satisfaction, which is assessed via a survey.

The aim of this registry to assess difference in patient satisfaction and rate of vascular and bleeding complications with use of either Perclose Proglide system or F08S for venous closure post atrial fibrillation ablation and atrial flutter ablation procedures in comparison to standard manual compression. If they are found to increase patient satisfaction as hypothesized, cardiac electrophysiologists can use VCD or F08S for access site closure instead of manual compression.

II. Research Plan and Design

A. Study Objectives: The objective of this registry is to find out if there is a difference in patient satisfaction and rate of vascular and bleeding complications with use of Perclose Proglide system or F08S for venous closure post atrial fibrillation and atrial flutter procedures in comparison to manual compression.

B. Study Type and Design: The design will be a prospective observational registry collecting data on patients who underwent catheter ablation for atrial fibrillation and atrial flutter, including administration of a patient survey.

C. Sample size, statistical methods, and power calculation

As a registry, there is no targeted enrollment, however it is expected that approximately 120 patients would be enrolled in 6 months.

D. Subject Criteria (See Vulnerable Populations appendix, if applicable):

1. Inclusion criteria:

- Patients undergoing a catheter ablation procedure (radiofrequency ablation or cryoablation) to treat symptomatic paroxysmal atrial fibrillation or atrial flutter.
- Patients willing to participate in a short written survey.

2. Exclusion criteria:

- Patients undergoing ablation for an arrhythmia other than atrial fibrillation/atrial flutter or who are not candidates for an ablation procedure for treatment of atrial fibrillation/atrial flutter.
- Patients who are not able to read or understand the English language.
- Patients who had recent access site complications within the same hospitalization.
- Patients who have baseline thrombocytopenia (platelet count less than 80) or known coagulopathy (INR > 1.5).

3. Withdrawal/Termination criteria:

No necessary safety precautions are to be applied to those who withdraw.

A study subject may participate in any another research study while participating in this registry.

E. Specific methods and techniques used throughout the study

Once approval from the Institutional Review Board is obtained, patients who underwent catheter ablation for atrial fibrillation or atrial flutter will be approached for inclusion in this registry. The morning after the procedure, patients will be requested to fill out informed consent documents, followed by a survey (Appendix A). This survey will include parameters such as their perception of pain following the procedure, discomfort experienced, any complications that may have occurred after the procedure, their preference if a repeat procedure was to be performed, as well the patient's overall satisfaction with the recovery process. A retrospective chart review of these patients would be done to assess for any complications in the post procedure period, such as bleeding, hematoma formation, pseudo-aneurysm, arterio-venous fistula etc. Other parameters to be measured include the time to achieve hemostasis, time to ambulate and length of hospital stay. These parameters are all recorded in the patient's clinical record as part of the standard of care.

F. Risk/benefit assessment:

Patients in this registry will not be exposed to any additional procedural risks as all treatments are in accordance with accepted clinical practice. The only potential risk would be a breach of Protected Health Information (PHI) confidentiality.

The potential benefit of participating in the study would be for the future patients undergoing catheter ablation procedures for atrial fibrillation and atrial flutter.

G. Location where study will be performed:

The morning after the procedure, patients in the cardiovascular recovery unit will be requested to fill out informed consent documents, followed by a survey (Appendix A). Each survey will be assigned a randomly generated confidential ID number and the data from the survey will be entered and analyzed into a spreadsheet that does not contain any patient identification information. A separate password protected spreadsheet will be maintained with an index of the randomly generated confidential ID numbers and the corresponding patient name and date of birth, however this will be stored separately and only the principal investigator will have access to this file.

H. Collaboration (with another institution, if applicable): N/A

I. Single IRB Review for a Multi-site study (if applicable): N/A**J. Community-Based Participatory Research (if applicable): N/A****K. Personnel who will conduct the study, including:**

1. Indicate, by title, who will be present during study procedure(s): [name]
2. Primary responsibility for the following activities, for example:
3. Determining eligibility: [name]
4. Obtaining informed consent: [name]
5. Providing on-going information to the study sponsor and the IRB: EP Research Coordinator and Regulatory Specialist
6. Maintaining participant's research records: EP Research Coordinator
7. Completing physical examination: [name]
8. Taking vital signs, height, weight: [name]
9. Drawing / collecting laboratory specimens: N/A
10. Performing / conducting tests, procedures, interventions, questionnaires: [name]
11. Completing study data forms: [name]
12. Managing study database: [name]

L. Assessment of Subject Safety and Development of a Data and Safety Monitoring Plan**III. Subject Participation**

A. Recruitment: The morning after the procedure, [name] will approach patients who underwent an ablation on the previous day and provide detailed information about the registry to the patients.

B. Screening Procedures or Interview/questionnaire: N/A

C. Informed consent process and timing of obtaining of consent

If the patient is agreeable to participate, [name] will request they fill out informed consent documents, followed by a survey (Appendix A). Patients will not be coerced into participation and it will be emphasized to the patient that participation is voluntary. If patients are unable to provide informed consent due to cognitive or psychiatric impairment, they will not be enrolled in the registry.

D. Alternatives to Participation: If patients decline participation, they will continue to receive post-procedure care in the usual manner.

E. Costs to Subjects: There are no costs to the subject that could be incurred as part of this research study

F. How new information will be conveyed to the study subject and how it will be documented: If new information becomes available that may potentially impact the study subject, they will be notified by the principal investigator, [name].

G. Payment, including a prorated plan for payment: Patients will not receive any payment for the study.

H. Payment for a research-related injury: There is no possibility of injury in this study.

IV. Data Collection and Protection

A. Data Management and Security: The morning after the procedure, patients will be requested to fill out informed consent documents, followed by a survey (Appendix A). This survey will include parameters such as their perception of pain following the procedure, discomfort experienced, any complications that may have occurred after the procedure, their preference if a repeat procedure was to be performed, as well

the patient's overall satisfaction with the recovery process. Each survey will be assigned a randomly generated confidential ID number and the data from the survey will be entered and analyzed into a spreadsheet that does not contain any patient identification information. A separate password protected spreadsheet will be maintained with an index of the randomly generated confidential ID numbers and the corresponding patient name and date of birth, however this will be stored separately and only the principal investigator will have access to this file. Once the survey data has been entered and confirmed, the original survey will be destroyed. A retrospective chart review of these patients would also be done to assess for any complications in the post procedure period, such as bleeding, hematoma formation, pseudo-aneurysm, arterio-venous fistula etc. Other parameters to be measured include the time to achieve hemostasis, time to ambulate and length of hospital stay. These parameters are all recorded in the patient's clinical record as part of the standard of care. All documentation related to the procedure will keep in a locked, secure file cabinet at St. Luke's Hospital and/or an encrypted, protected electronic storage device that can only be accessed by participating investigators.

B. Sample / Specimen Collection: N/A**C. Tissue Banking Considerations: N/A****D. Procedures to protect subject confidentiality:** All documentation related to the procedure will be kept in a locked, secure file cabinet at St. Luke's Hospital and/or encrypted, protected electronic storage device that can only be accessed by participating investigators.**E. Quality Assurance / Monitoring**

1. At the time of data collection, Drs. [name] and [name] will review the data together to ensure that it is entered correctly from the survey into the spreadsheet. Any discrepancy will be analyzed before the original paper form is discarded.

V. Data Analysis and Reporting**A. Statistical and Data Analysis:** Categorical variables will be compared with Chi-Square analysis. The patient factors that may contribute to the outcomes listed

below will be analyzed via logistic regression with subsequent multivariate logistic regression designed to compare these risk factors.

B. Outcome: The main outcomes of interest are

- Perception of pain during recovery process
- Overall satisfaction with recovery process
- Time to achieve hemostasis
- Time to ambulate following hemostasis

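### Complication rates are open to selection on the outcome, because the chart review covers only patients who agree to consent and a survey the morning after ablation

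*Combined protocol and SAP*

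**What the plan says.** Section III.A has a member of the team who "will approach patients who underwent an ablation on the previous day and provide detailed information about the registry". Section II.G gives the time and place: on the next morning, "patients in the cardiovascular recovery unit will be requested to fill out informed consent documents", with the survey to follow. Section III.C goes on to consent only "If the patient is agreeable to participate", and adds: "If patients are unable to provide informed consent due to cognitive or psychiatric impairment, they will not be enrolled in the registry". Survey willingness is itself an inclusion criterion in section II.D.1: "Patients willing to participate in a short written survey". Section II.D.2 excludes this group: "Patients who are not able to read or understand the English language".

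The complication data come from the same people. Section II.E states: "A retrospective chart review of these patients would be done to assess for any complications in the post procedure period". Section IV.A repeats this. For patients who decline, section III.D describes usual care and no data collection.

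The complication rate is a comparative aim: it is in the hypothesis (I.A), the objective (II.A) and the main outcomes (V.B). Section I.B has manual compression and closure-device patients watched overnight for access-site problems, which is before the consent approach. The plan has no consecutive-enrolment rule, no log of patients not enrolled and no count of enrolment by closure method. Section V.A lists chi-square tests and logistic regression, with nothing on non-participation.

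**The concern.** Entry comes after both the exposure and much of the early outcome. A patient who bled overnight may be too unwell, too unhappy with recovery, or simply not available when consent is sought. That patient then drops out of the numerator and the denominator of the complication rate. Recovery also differs by method (section I.B describes much longer bed rest after manual compression than after a closure device), so willingness to take part need not respond to a complication in the same way in each group. Adjusting for measured patient factors cannot bring back patients who never entered.

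At stake is one of the registry's two stated objectives, the comparison of vascular and bleeding complications between methods. The chart outcomes do not need this restriction. Sections II.E and IV.A say that hemostasis time, ambulation time and length of stay are recorded as standard of care. Additional compression is not asked about in the survey, so it too must come from the chart.

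**Working it through.** **The plan's own figure.** Section II.C expects about 120 patients in 6 months and says that there is no target. No rate, effect size, power or group split is given, so there is nothing to reproduce.

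**Inputs.** The documents give no complication rate and no participation rate. All values of p, c1 and c0 below are assumptions.
- p: true complication rate
- c1: probability of enrolling with a complication
- c0: probability of enrolling without one

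**Formulas.**
- Observed rate = p·c1 / [p·c1 + (1−p)·c0]
- Observed odds ratio = true odds ratio × (c1/c0 in method A) / (c1/c0 in method B)

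**Equal selection in every method**, p = 6%, c0 = 90%, c1 = 50%:
- 0.06×0.5 = 0.030 and 0.94×0.9 = 0.846
- Observed rate = 0.030/0.876 = 3.4%
- c1/c0 is the same in each method, so the odds ratio is unchanged.

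**Selection that differs by method**, p = 6% in both, c0 = 90% in both:
- Method A, c1 = 70%: 0.042/(0.042+0.846) = 0.042/0.888 = 4.7%
- Method B, c1 = 40%: 0.024/(0.024+0.846) = 0.024/0.870 = 2.8%
- Rate ratio = 1.71 where the truth is 1 (0.58 if the methods are swapped); odds ratio = 0.70/0.40 = 1.75

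**Range for equal selection**, c0 = 90%:

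| True rate | Observed, c1 = 70% | Observed, c1 = 45% |
|---|---|---|
| 2% | 1.6% | 1.0% |
| 5% | 3.9% | 2.6% |
| 10% | 8.0% | 5.3% |

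**Range for differing selection**, true odds ratio 1.0:
- c1/c0 of 0.5 in both methods gives 1.0.
- 0.8 against 0.5 gives 1.6.
- 1.0 against 0.5 gives 2.0, or 0.5 with the methods swapped.

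**Would enrolment by method reveal the problem?** In the 70% against 40% scenario, overall enrolment is 0.042+0.846 = 88.8% in one method and 0.024+0.846 = 87.0% in the other. The two look alike although the observed rates differ 1.7-fold.

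**Scale.** At 6%, 120 patients give 120×0.06 = 7.2 events. Split equally over three methods, that is 40×0.06 = 2.4 each. One or two missed events would alter the comparison.

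**With all eligible ablations included**, c1 = c0 = 1, so the observed rate equals the true rate and this distortion of the odds ratio disappears.

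**The case against.** A reader might infer that the rates are in fact selected on the outcome and too low. The documents do not show that. Nothing in them says that complicated or dissatisfied patients enrol less; some may be keener to answer a survey about their recovery. Selection is possible and unmonitored, and no more than that can be said.

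Nor is the whole outcome known at consent. Survey answers follow consent. Length of stay may be incomplete, and the post-procedure period has no stated end, so later complications can still appear. The overnight monitoring in section I.B is stated for manual compression and the closure device only, and the figure-of-8 stitch is not cut until the following day.

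Two of the entry conditions carry less weight than they seem to. The recovery-unit wording stands under a heading about location, while section III.A names no unit; it may describe the usual place and not an entry criterion. The English requirement precedes the procedure and is not caused by a complication, so it limits generalizability but is not selection on the outcome.

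Finally, the illustration returns what is put into it: the ratio of 1.71 is close to 70/40. With so few events, chance would dominate the comparison in any case. Surveying consenters is also a reasonable design for satisfaction, which is the basis for the practice change envisaged in section I.C.

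All of this stands, and it narrows the point. It does not remove it: even if every patient is approached, agreement and survey willingness still come after the early outcome, and those who do not agree contribute no complication data.

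**Conclusion.** The point holds as a weakness of design. Chart-derived complication rates are open to outcome-dependent selection that the plan neither prevents nor measures. Understated rates require that complicated patients enrol less often. A biased comparison further requires that the shortfall differ by closure method, and it could then favor either one. Size and direction cannot be derived from the documents; 6% appearing as 3.4%, or as 4.7% against 2.8%, shows only what moderate assumed differences would do.

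The point does not depend on the exclusion in section II.D.2 of recent access-site complications within the same hospitalization. That exclusion's timing relative to the index ablation is undefined and is a separate matter. The calculations assume that it does not remove complications of the index procedure. The change is worth making because it is cheap and closes a real route to bias.

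**What to change.** Define two populations in sections II.D, II.E and V.

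1. **Chart-derived outcomes** (time to hemostasis, time to ambulation, complications, additional compression, length of stay): every consecutive otherwise eligible atrial fibrillation or flutter ablation in the period, by de-identified abstraction under an IRB waiver of consent.
2. **Survey outcomes** (pain, satisfaction and the other survey items): apply consent, survey willingness and the English requirement here only.

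Whether a waiver can be had is for the IRB. If it is refused, keep a log of all ablations with closure method, whether approached, reason not enrolled and, as the IRB permits, access-site complication yes or no. Report enrolment by method and complication status together, since enrolment by method alone can look balanced while the rates are distorted. Describe the complication rates as applying to consenting survey respondents only.

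The cost is a waiver request and modest extra chart time for patients who do not take the survey.

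### Closure method is not randomised, yet the only planned comparison that fits the objective is an unadjusted chi-square that ignores the order of the survey answers

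*Combined protocol and SAP*

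**What the plan says.** - **Design (II.B):** "The design will be a prospective observational registry collecting data on patients who underwent catheter ablation". Staff "will approach patients who underwent an ablation on the previous day" (III.A), so closure is already done when a patient is enrolled. No section gives randomisation, matching, or a rule for who receives manual compression (MC), the closure device (VCD) or the figure-of-8 stitch (F08S).
- **Objective and use (II.A, I.C):** VCD or F08S is compared with MC on satisfaction and on complications. If satisfaction is found to be higher, "cardiac electrophysiologists can use VCD or F08S for access site closure instead of manual compression".
- **Analysis (V.A):** "Categorical variables will be compared with Chi-Square analysis", with no grouping named. The second sentence takes as its subject "The patient factors that may contribute to the outcomes listed" and then sets out the method: "below will be analyzed via logistic regression with subsequent multivariate logistic regression designed to compare these risk factors". No exposure, reference group, contrast or covariate is given.
- **Data:** Satisfaction and pain are five-level ordered items (Appendix A, items 1 and 3). The chart review in II.E and IV.A lists complications and adds "Other parameters to be measured include the time to achieve hemostasis, time to ambulate and length of hospital stay". All of these are outcomes.
- **Size (II.C):** There is no target, but "it is expected that approximately 120 patients would be enrolled in 6 months".

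**The concern.** The registry asks a comparative question about a treatment that clinicians chose. Anything that influenced the choice and also affects how a patient rates recovery would distort a crude comparison. The documents themselves describe pre-closure features that vary between patients: sheath number and size and anticoagulant handling (I.B), radiofrequency or cryoablation and fibrillation or flutter (II.D), and prior ablation with MC (survey item 4).

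The planned regression could deal with the measured ones, but its stated purpose is to compare risk factors, and closure method is a treatment rather than plainly a patient factor. Followed literally, V.A would leave the practice message in I.C resting on an unadjusted test. That test also discards the ordering of the answers, which costs power.

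**Working it through.** The plan has no derived figure to reproduce, since 120 is an accrual expectation. The calculation below illustrates how far a crude test could mislead. **Every input except the total of 120 is assumed.**

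**1. Inputs.** An equal split gives 120 / 3 = 40 per method. There is no true closure effect. One binary pre-closure factor divides the odds of satisfaction by 2, 3 or 4. Satisfaction without the factor is b = 60%, 80% or 90%. Tests are two-sided at 0.05.

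**2. Spurious difference.** With odds ratio R, satisfaction among patients with the factor is q = o / (1 + o), where o = [b / (1 − b)] / R. In a group with factor prevalence p, satisfaction is p·q + (1 − p)·b. For b = 0.60 and R = 4:
- o = 1.5 / 4 = 0.375, so q = 0.375 / 1.375 = 0.273.
- MC at p = 0.70: 0.70 × 0.273 + 0.30 × 0.60 = 0.371.
- Closure group at p = 0.30: 0.30 × 0.273 + 0.70 × 0.60 = 0.502.
- Difference: 0.502 − 0.371 = +0.131. Swapping the prevalences gives −0.131.

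The sign therefore depends entirely on which group carries the factor more often.

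**3. Rejection rate if the item is dichotomised** (exact enumeration, 40 v 40, uncorrected Pearson chi-square; ranges over R = 2 to 4):

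| Prevalence MC / closure | b = 60% | b = 80% | b = 90% |
|---|---|---|---|
| 50 / 50 | 5.5–5.7% | 4.8–5.0% | 5.1–5.4% |
| 50 / 40 | 5.9–6.6% | 5.2–5.7% | 5.6–5.8% |
| 60 / 30 | 8.3–15.4% | 6.9–13.3% | 6.7–10.9% |
| 70 / 30 | 10.4–23.1% | 8.3–20.0% | 7.5–15.2% |

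**4. Rejection rate on the item as collected.** V.A states no cut-point, so chi-square on the five levels is the more literal reading. The assumed level shares, worst to best, were .03/.07/.30/.40/.20, .01/.04/.15/.45/.35 and .01/.02/.07/.40/.50. With R = 2 and 4 at 60/30 and 70/30, simulation of the 2×5 test gave 4.3% to 13.5%, and a second simulation 4.4% to 13.1%. At R = 2 nothing exceeded 6.8%. Sparse cells make this test somewhat conservative, but the point estimate is still confounded.

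**5. What adjustment does.** In a proportional-odds model with closure method (2 parameters) and four covariates, over the same settings, rejection was 5.1% to 6.3% with the factor included and 8.6% to 26.6% with it omitted. The closure standard error was 1.05 to 1.09 times the unadjusted one. Measurement matters: in the binary version at b = 60% and 70/30, recording the factor with 20% misclassification still left 7.7% to 13.3%.

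**6. What the ordering is worth.** At an assumed closure odds ratio of 3 and 40 v 40, power was about 0.46 to 0.51 for the 2×5 chi-square and 0.66 to 0.74 for an unadjusted rank test. With no imbalance, at 60 / 80 / 90% satisfied:

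| Analysis | 60% | 80% | 90% |
|---|---|---|---|
| Adjusted ordinal | .79 | .76 | .69 |
| Adjusted binary | .65 | .43 | .12 |
| Unadjusted chi-square, dichotomised | .63 | .48 | .27 |

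**7. Room for covariates.** Six parameters is already a sizeable model here. The ordinal effective size, n − Σnᵢ³/n², is 108, 104 and 97 for the three distributions, or 18, 17 and 16 per parameter. It falls to 58 / 6 = 9.7 if 80% choose the top level (.01/.01/.03/.15/.80). A binary outcome at 90% satisfied has 12 in the smaller class, or 12 / 6 = 2 per parameter.

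**The case against.** The strongest case for the plan has four parts.

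- **A multivariable model is already planned, and closure method is a natural term in it.** This stands in part. A reader might infer that no adjustment is intended, and the documents do not support that, because V.A leaves closure method neither in nor out. But a model with no named exposure or covariates does not commit anyone to an adjusted contrast.
- **No imbalance is shown.** This is correct. A reader might infer that the comparison will be biased, or biased towards VCD and F08S. No section says that any factor differs by closure method, and mild imbalance has little effect.
- **Useful data exist.** This is also correct. Date of birth is held in the index file (II.G, IV.A), and survey item 4 records prior ablation with MC. II.K assigns staff to vital signs, height and weight. II.D already excludes low platelets, known coagulopathy and recent access-site complications. The chart-review list is plainly not exhaustive, since it omits protamine use and additional compression, both outcomes in V.B. A reader might infer that baseline data will not be collected, but the text shows only that they are not specified.
- **The stakes are modest.** The wording in I.C is permissive and carries no significance rule. That limits the severity, but the crude difference would still be the stated support for the message.

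**Conclusion.** The point holds as a gap in the stated analysis with a better method available at low cost. Closure method is not randomised, and V.A commits only to a comparison that is unadjusted and ignores order. Confounding of the satisfaction contrast is possible; its size and direction cannot be obtained from the documents.

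Under strong assumed imbalance (60/30 to 70/30, odds ratio 2 to 4), false rejection is about 4% to 13% for the five-level chi-square. The figure of about 7% to 23% applies only if the item is dichotomised, which V.A does not state, so it should not be read as the error rate of the plan. All these rates rest on an equal split, a single binary factor and assumed satisfaction levels.

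The sponsor should make the change, but the data remain usable without it. Confidence is medium, because materiality depends on imbalances not yet seen.

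**What to change.** In V.A, make the main analysis of satisfaction and pain a proportional-odds logistic regression with closure method as the exposure (MC as reference, VCD, F08S).

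- **Covariates.** Adjust for a short list of pre-closure factors, fixed before outcomes are viewed by closure method and small enough for about 120 patients. Examples are age (from date of birth), prior ablation with MC (survey item 4), ablation type, and sheath number or size.
- **Protamine.** Do not adjust for it. It is part of the F08S technique (I.B) and a listed outcome (V.B).
- **Data.** Add closure method and the chosen fields to the planned chart review, and tabulate them by closure method.
- **Reporting.** Keep chi-square as a secondary analysis, and word the conclusion as an association.

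The cost is a rewording of V.A, a few more fields in a review already planned, and a closure standard error about 5% to 9% larger in the ordinal illustration. Confounding by unrecorded or poorly recorded factors remains. A dichotomised adjusted model is not an equal substitute: at 80% and 90% satisfied its power was .43 against .48, and .12 against .27, compared with the unadjusted chi-square.
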